BMI	Body mass index

KEYWORDS

COX-2, prostacyclin, ibuprofen, Vioxx, thrombosis, nitric oxide, ADMA, L-arginine

STUDY SUMMARY

TITLE COX-2/prostacyclin/ADMA/NO axis in the cardiovascular system

DESIGN Two arm, single centre mechanistic study. Subjects will be computer randomised to either arm.

AIMS

- To perform a systemic analysis of how COX-2 inhibition by celecoxib affects vascular function and 'omic biomarkers including those associated with the COX-2/prostacyclin/ADMA axis in healthy male volunteers
- To investigate how this is altered by L-arginine supplementation

OUTCOME MEASURES

Primary endpoint: endothelial function measured using EndoPAT

Secondary endpoints: Blood pressure, cardiovascular biomarkers, eicosanoid and methylarginine/amine levels, plasma proteome and blood transcriptome

POPULATION Healthy male volunteers

ELIGIBILITY

Inclusion Criteria	Exclusion Criteria

 • Male, 18-40 years old • No abnormal findings on medical history, screening, physical examination, haematology, biochemistry, urinalysis and vital signs (sitting blood pressure, resting pulse rate, respiratory rate and body temperature within two weeks of commencement date) • Normal fasting lipid profile (Soverson et al, 1994) • Non-smoking • Clear venous access in upper limbs • BMI 18-30 • No history or signs of drug abuse • No other medication 4 weeks before or during study • Informed written consent 	
 • Any history of allergy to NSAIDs or arginine • Significant medical conditions • Pulse rate<50 beats/minute • Sitting systolic blood pressure <80 or >160 mmHg • Sitting diastolic blood pressure <60 or >100 mmHg • Baseline endothelial dysfunction (as defined by EndoPAT; LnRHI<0.51) • Participation in other clinical study 8 weeks before or during study • Donation of blood 8 weeks before or during study • COVID-19 vaccination within 4 weeks • Positive COVID-19 test

TREATMENT

[figure not shown]
Celecoxib: 200 mg b.i.d (400mg total/day)

L-arginine 5g b.i.d. (10g total/day)

Celecoxib, L-arginine or placebo will be dispensed against an individual prescription by a registered pharmacist. Drugs will be stored at the Imperial/NIHR Clinical Research Facility. Drugs or placebo will be administered orally.

DURATION 7 days of active treatment in each study arm (see flowchart below)

STUDY FLOWCHART AND TIMELINE

Exam	Visit number	1	2	3	4
	0 (Screening)				
Informed consent	x				
Medical history	x				
Physical exam/questionnaire	x				
Blood pressure	x	x	x	x	x
Heart rate	x	x	x	x	x
Breathing rate	x				
Temperature	x				
Height	x				
Weight	x				
Urine sample	x	x	x	x	x
Blood sample 50ml	x	x	x	x	x
EndoPat	x	x	x	x	x
Study medication(s) dispensed		x		x	

ANALYSIS/STORAGE OF SAMPLES

Samples will be stored in freezers or refrigerators or other appropriate place within secure, swipe access only facilities at Imperial College London. Results obtained during the study which will be stored on University Computers (including University Laptops) in a pseudonymised format; as part of our study we will measure gene expression and a large number of different proteins and other mediators in the volunteer's blood. Under GDPR (Recital 34) the gene expression data that we measure is classified as 'identifiable personal data'. However, the type of analysis that we are performing involves RNA and not genomic DNA which means that it would not be possible for a 'motivated individual with no special skill in genetics and no access to non-public datasets' to be able to identify individuals. Furthermore, we have performed a data-protection risk assessment on this study.

We will also send samples for analysis to collaborators within and outside of the EEA. All samples and data will be coded before leaving the study team. For some measurements the samples will be sent to service providers under contracts and for others to academic collaborators. All samples would be pseudonymised before leaving the study team and analysis conducted either done under contract for payment and/or as part of an academic collaboration. Where required a transfer agreement will be in place. Samples will be stored for future use subject to any requirement for future ethical approval.

1. INTRODUCTION

1.1. BACKGROUND

Cyclooxygenase-2 (COX-2) is an inducible enzyme expressed in inflammation and cancer. However, COX-2 in discreet regions including areas of the vasculature and in the kidney^{1, 2} is a powerful cardiovascular protective pathway that works via formation of prostacyclin. In blood vessels, prostacyclin acts on smooth muscle and platelets to produce vasodilation and platelet inhibition, and in the kidney, regulates renal function and vasoactive hormone pathways to indirectly affect the systemic vasculature. These cardiovascular protective roles of COX-2 and prostacyclin are illustrated by the fact that nonsteroidal anti-inflammatory drugs (NSAIDs), which work by blocking COX-2 and include some of the world's most commonly taken drugs, cause the high profile cardiovascular side effects that have led to black box warnings on all drugs in this class^{2, 3}.

It was initially thought that cardiovascular side effects were limited to drugs that selectively target COX-2³⁻⁵, such as Vioxx® (rofecoxib) and Celebrex® (celecoxib), introduced in the early 2000's^{6, 7}. However, as a result of subsequent epidemiology analyses^{8, 9} and, most recently, the publication of two large clinical cardiovascular outcome studies, SCOT¹⁰ and PRECISION¹¹, it is clear that traditional NSAIDs, including ibuprofen and naproxen, carry at least as great a cardiovascular risk as the COX-2 selective drug celecoxib with ibuprofen, which is remarkably still an over the counter medication, emerging as significantly more toxic to the kidney¹¹.

The scale of use of NSAIDs (estimated to be regularly taken by 20-30% of the population) and the degree of associated risk (increased by 30%¹²) means that these drugs are a significant risk factor for heart attacks and strokes in their own right, potentially accounting for up to 50,000 of the 458,000 heart attacks and strokes in the UK each year (Jan 2016). Moreover, we now know that this risk emerges with just 1-2 weeks of use¹³. Concern over adverse cardiovascular events caused by NSAIDs has led to cautious prescribing of COX-2 selective NSAIDs in favour of older NSAIDs, which are more toxic to the gut, or opioids, which carry problems of tolerance, addiction and additional health burdens, and to the withdrawal in Europe of celecoxib for the prevention of colon cancer.

Mediators of protection: the power of arginine as a therapy

Endothelial nitric oxide synthase (eNOS) is expressed throughout the vasculature where it protects the entire cardiovascular system against atherosclerosis, thrombosis and hypertension. The power of eNOS and COX-2 together in protecting the cardiovascular system is biologically enhanced since NO and prostacyclin work additively to maintain vascular function and in a synergistic manner against thrombosis¹⁴. Thus, this pathway, which links COX-2 with prostacyclin and eNOS, provides a plausible mechanism that explains how NSAIDs precipitate cardiovascular side effects. This is supported by our¹⁵ and others'¹⁶ previously published findings showing that loss of COX-2 in mice is sufficient to impair systemic eNOS function in blood vessels *ex vivo*^{15, 16} and that this was rescued by supplying the eNOS substrate L-arginine *in vitro*¹⁵.

Whilst this provides essential proof of concept data we now need to complete and expand this work. In addition to basic science research, we need to translate these findings into man. We will do this by conducting a clinical study in healthy male volunteers using a study design model based on our previous work¹⁵ that will determine the effects of COX-2 inhibition on cardiovascular endpoints and their sensitivity to reversal by L-arginine.

These data will provide essential information on (i) how COX-2 inhibition and the COX-2/prostacyclin/ADMA axis effect vascular function and (ii) the potential of L-arginine as a rescue therapy for NSAID cardiovascular toxicity.

1.2. RATIONALE FOR CURRENT STUDY

Hypothesis: COX-2 inhibition compromises endothelial function, which can be prevented by L-arginine.

2. STUDY OBJECTIVES

Investigate arginine as a means of preventing or alleviating the detrimental effects of celecoxib on measured functional endpoints and biomarkers.

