3. STUDY DESIGN

Two arm, single centre mechanistic study.

Forty healthy male volunteers, twenty in each arm.

Primary endpoint: Endothelial function measured using EndoPAT

Secondary endpoints: Sitting blood pressure, cardiovascular biomarkers, eicosanoid and methylarginine/amine levels, plasma proteome and blood transcriptome.

Functional Endpoints	Biomarkers

 • EndoPAT- endothelial function • Blood pressure 	
 • Methylarginines- ADMA, SDMA and L-NMMA • Amino acids- full range including L-arginine, L-ornithine, L-citrulline. • Eicosanoids- full range including prostacyclin and PGI-M • Cardiovascular Biomarkers- thromboxane, endothelin-1, nitric oxide, renin, angiotensin, apolipoproteins, D-dimer, Sicam-1 and CRP • Renal biomarkers- creatinine, urea, cystatin C, KIM-1 and albumin

Healthy male volunteers will be randomized to 7 days' treatment with celecoxib (200mg b.i.d.; the standard maximum anti-inflammatory dose) or placebo in a double blinded format. Samples and measurements will be made at baseline and after the final dose. Following a washout of at least 4 weeks, L-arginine (Lambers Healthcare Limited) may be administered in a dose of 5g b.i.d. (10g total/day) as per the study flowchart (page 5). A rational approach was taken in selecting the arginine dose since 10g/day increases plasma arginine by $\approx 40\%$ ¹⁷. At each visit, the primary endpoint will be endothelial function, measured using EndoPAT, which measures changes in flow-mediated endothelial function in the microvasculature. Importantly, EndoPAT is clinically validated with scores that correlate with cardiovascular risk¹⁸. Additionally, at each study visit, blood pressure, cardiovascular biomarkers (by ELISA) and

eicosanoid and methylarginine/amine levels (by GC/LCMS/MS) will be measured. Samples will also be collected for measurement of 'omic' biomarkers including transcriptomics, proteomics, lipidomics and metabolomics. Additionally volunteers will monitor and record their blood pressure readings daily using a home monitoring device and protocols validated and suggested (respectively) by the British and Irish Hypertension Society. In vivo aspects of this study will be performed using validated protocols¹⁵ and using facilities and staff at the NIHR/Wellcome Trust Imperial College Clinical Research Facility.

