Once participants are enrolled and randomised in the study, the study visits (visits 1 & 2 in phase 1 and visits 3 & 4 in phase 2) need to occur exactly 7 days apart. If participant attends visit 1 but is unable to attend visit 2 for a reason that is unrelated to the study medication e.g. develops an unrelated illness or cannot attend for personal reasons, the participant will have the option to re-enrol as a new participant if there is at least a 4-week washout period if they wish to do so. These participants will need to re-attend screening and re-consent and will be treated as a new participant with a new study number. To avoid double counting, any data obtained from the initial enrolment will not be used and will be superseded by the data generated by re-enrolment.

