7. STATISTICS AND DATA ANALYSIS

Sample size: This is a novel mechanistic study where the primary endpoint is the effect of celecoxib on endothelial function measured using the EndoPAT device. We anticipate that we will require n=20-40 in each study arm to detect a difference based on previous work using similar drugs and alternative measurement approaches. For example Carlsson and Wennmalm (1983)¹⁹ showed a reduction in endothelial function with ibuprofen (effect size: 0.80 standard deviations) and diclofenac (effect size: 1.06 standard deviations). This equates to a power of 72-92% at n=20 and 95-100% at n=40 to detect a difference between groups at a nominal significance threshold of p<0.05. As we are using a different drug and an alternative measurement platform, power can only be estimated broadly. As such, we will perform an interim analysis of data after studying n=20 volunteers per group during the 'wash out' period. At this point, actual effect size and variance will be determined and experimental power re-calculated. If our primary endpoint is not achieved, we may revise our endpoints and/or if additional power is required, we will reserve the option to recruit up to an additional n=20 volunteers per group. Dependent upon the results the interim analysis may also serve as a stop-go checkpoint for continuation of the L-arginine arm of the study.

Data analysis: Data will be analysed according to approaches applicable to the measurement. This includes standard parametric and non-parametric tools (including Fisher's exact tests, Student's t-tests, 1-way and 2-way ANOVAs, Mann Whitney U-tests and Kruskall-Wallis tests) as well as specialised tests for large omic data sets (including modified t-test with false discovery correction where appropriate). Across all tests differences will be considered significant where p<0.05.

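### Does section 7 need to name an L-arginine contrast and a paired test, given that L-arginine rescue is the section 2 objective?

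*Combined protocol and SAP*

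**What the plan says.** L-arginine is prominent in the aims. Section 2 has a single objective, "Investigate arginine as a means of preventing or alleviating the detrimental effects of celecoxib on measured functional endpoints and biomarkers". The hypothesis in section 1.2 is that "COX-2 inhibition compromises endothelial function, which can be prevented by L-arginine". The second aim in the study summary is "To investigate how this is altered by L-arginine supplementation".

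The design gives L-arginine in the second phase. Section 3 begins that step "Following a washout of at least 4 weeks, L-arginine" and makes it optional, referring to the study flowchart for the arrangement. Section 4 (Re-enrolment) describes "visits 1 & 2 in phase 1 and visits 3 & 4 in phase 2". The natural reading is that each volunteer passes through both phases.

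Section 7 states that "the primary endpoint is the effect of celecoxib on endothelial function measured using the EndoPAT device", and all its power figures concern that comparison. L-arginine appears there only as something the interim analysis may stop or continue. The data analysis paragraph says that methods will fit the measurement. It then lists, as inclusions, Fisher's exact test, the t-test, one- and two-way ANOVA, Mann-Whitney, Kruskal-Wallis and a modified t-test for omics.

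**The concern.** An objective without a named comparison leaves the analyst to choose one, possibly after seeing phase 1 data. Several comparisons are available and their power differs widely. No listed test is said to be paired or repeated-measures. One-way ANOVA and Kruskal-Wallis need three or more groups to add anything to a two-sample test, and in a two-arm trial the obvious groups are arm-by-phase cells, which share volunteers. Treating those cells as independent would waste the within-volunteer information. An omnibus test over them would also not isolate rescue: under the assumptions below, a one-way ANOVA over the four cells is significant in 79/76/73% of trials when L-arginine does nothing and in 72/71/70% when it reverses the effect fully. What would be at stake is a missed or uninterpretable answer to the section 2 objective.

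**Working it through.** **1. The plan's own figure.** Two-sided normal approximation, n per arm, SD 1: power = Φ(d√(n/2) − 1.96).
- n=20: d=0.80 gives Φ(2.530 − 1.96) = 71.6%; d=1.06 gives Φ(3.352 − 1.96) = 91.8%.
- n=40: 94.7% and 99.7%.

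These match the stated 72–92% and 95–100%. They cover celecoxib against placebo only.

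**2. Inputs for an L-arginine illustration.** From section 7: n=20 per arm and a 0.80 SD celecoxib effect. Assumed, because the documents do not give them: between-phase correlation r = 0.3/0.5/0.7; arms keep celecoxib or placebo in phase 2 and both receive L-arginine; no carry-over; L-arginine reverses the effect fully.

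**3. Three defensible contrasts.** All use within-volunteer differences (two-sided 5%, noncentral t). The second also assumes equal correlation r among all four visits.

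| Contrast | Variance per volunteer | Standardised effect | Power |
|---|---|---|---|
| Visit 4 − visit 2, between arms | 2(1−r) | 0.676/0.800/1.033 | 55/69/89% |
| (Visit 4 − 3) − (visit 2 − 1), between arms | 4(1−r) | 0.478/0.566/0.730 | 31/41/61% |
| Visit 4 − visit 2, celecoxib arm only, paired | 2(1−r) | 0.676/0.800/1.033 | 82/92/99% |

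The two between-arm rows use 38 degrees of freedom and noncentrality (effect × √10). The paired row uses 19 and (effect × √20).

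**4. They answer different questions.** Suppose L-arginine adds 0.80 SD in both arms. Celecoxib volunteers then return to the phase 1 placebo level, and the celecoxib-arm paired test is significant in 82/92/99% of trials. The visit 4 − visit 2 comparison between arms is significant in only 5%, because nothing differs between arms. Conversely, the celecoxib-arm test cannot separate L-arginine from a phase effect. Section 2 covers both prevention and alleviation and does not settle this.

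**5. Cost of ignoring the pairing.** An independent two-way ANOVA interaction on the visit 2 and visit 4 values, by simulation, has power 41/39/37% for full reversal, against 55/69/89% in the first row. Its type I error is 2.1/0.7/0.1%. At r=0 there is no loss (42% against 41%).

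**6. Does proceeding only after a positive phase 1 inflate false rescue claims?** With a true 0.80 SD celecoxib effect and no L-arginine effect, the chance that visit 4 − visit 2 is significant towards rescue, given a significant phase 1, is about 3.5%. Phase 1 is significant in about 69% of trials, so over all trials the rate is 0.69 × 3.5% = 2.4%, within the one-directional 2.5%. Section 7 also sets no significance-based rule for going on.

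**7. Does the text prescribe a wrong test?** No. A paired t-test is a form of Student's t-test, and a repeated-measures two-way ANOVA is a two-way ANOVA. The list is open, serves every endpoint and omics set, and does not assign one-way ANOVA or Kruskal-Wallis to arm-by-phase cells.

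**The case for a change.** The strongest case for a change is that L-arginine rescue is the only objective in section 2, so calling the study mechanistic does not excuse leaving its comparison open. Power in the table runs from 31% to 99% according to contrast and correlation, so the choice matters. Naming a contrast before the interim look would cost only a sentence and would remove any suspicion of choosing after the fact.

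The facts behind this stand: section 7 does not choose, and choosing beforehand is good practice. Two things limit the point. First, the phase 2 allocation cannot be read from the text available. The summary speaks of "7 days of active treatment in each study arm", and section 7 calls L-arginine an arm, so even the meaning of arm is uncertain. If L-arginine were randomised within phase 2, an unpaired comparison at visit 4 could be valid. Second, any single contrast put forward is a scientific choice among estimands and does not repair an error. The freedom in section 7 to revise endpoints at the interim is a separate matter, and naming an L-arginine test would not resolve it.

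**Conclusion.** No change follows. The plan omits detail on the L-arginine comparison but states no wrong analysis, and its open list already contains valid methods for repeated measurements. An analyst with four visits per volunteer and the study flowchart would use within-volunteer differences as a matter of course. The lapse feared, treating repeated values as independent, is hypothetical. It would err towards missed effects: a loss of 14 points of power at r=0.3 (55 − 41), 30 at r=0.5 (69 − 39) and 52 at r=0.7 (89 − 37), with type I error below 5% throughout. Those sizes rest on correlations and a phase 2 layout that the documents do not give. The choice among the three contrasts is open to debate, and the documents give no basis for imposing one.

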3. STUDY DESIGN

Two arm, single centre mechanistic study.

Forty healthy male volunteers, twenty in each arm.

Primary endpoint: Endothelial function measured using EndoPAT

Secondary endpoints: Sitting blood pressure, cardiovascular biomarkers, eicosanoid and methylarginine/amine levels, plasma proteome and blood transcriptome.

Functional Endpoints	Biomarkers

 • EndoPAT- endothelial function • Blood pressure 	
 • Methylarginines- ADMA, SDMA and L-NMMA • Amino acids- full range including L-arginine, L-ornithine, L-citrulline. • Eicosanoids- full range including prostacyclin and PGI-M • Cardiovascular Biomarkers- thromboxane, endothelin-1, nitric oxide, renin, angiotensin, apolipoproteins, D-dimer, Sicam-1 and CRP • Renal biomarkers- creatinine, urea, cystatin C, KIM-1 and albumin

Healthy male volunteers will be randomized to 7 days' treatment with celecoxib (200mg b.i.d.; the standard maximum anti-inflammatory dose) or placebo in a double blinded format. Samples and measurements will be made at baseline and after the final dose. Following a washout of at least 4 weeks, L-arginine (Lambers Healthcare Limited) may be administered in a dose of 5g b.i.d. (10g total/day) as per the study flowchart (page 5). A rational approach was taken in selecting the arginine dose since 10g/day increases plasma arginine by $\approx 40\%$ ¹⁷. At each visit, the primary endpoint will be endothelial function, measured using EndoPAT, which measures changes in flow-mediated endothelial function in the microvasculature. Importantly, EndoPAT is clinically validated with scores that correlate with cardiovascular risk¹⁸. Additionally, at each study visit, blood pressure, cardiovascular biomarkers (by ELISA) and

eicosanoid and methylarginine/amine levels (by GC/LCMS/MS) will be measured. Samples will also be collected for measurement of 'omic' biomarkers including transcriptomics, proteomics, lipidomics and metabolomics. Additionally volunteers will monitor and record their blood pressure readings daily using a home monitoring device and protocols validated and suggested (respectively) by the British and Irish Hypertension Society. In vivo aspects of this study will be performed using validated protocols¹⁵ and using facilities and staff at the NIHR/Wellcome Trust Imperial College Clinical Research Facility.

4. PARTICIPANT ENTRY

Pre-registration evaluations and study evaluations

We will advertise for volunteers within Imperial College London by email advertisements, noticeboards and social media and using the established healthy volunteer database at the NIHR/Wellcome Trust Imperial College Clinical Research Facility. A research nurse or other suitably qualified person will explain the study to interested volunteers and go through the participant information sheet with them, giving the volunteer an opportunity to ask any questions regarding the study. If the volunteer consents to the study they will sign the study consent form and will be given a copy of the participant information sheet to keep.

The volunteer will then undergo a screening assessment to check eligibility (fulfilment of inclusion/exclusion criteria). This will include:

- Medical history questionnaire, including questions of history of drug abuse
- Sitting blood pressure, heart rate, respiratory rate and temperature
- Height and weight to calculate BMI
- Blood sample to measure routine haematology and biochemistry (including lipid profile)
- Urine sample to measure glucose and specific gravity
- EndoPAT measurement to confirm normal endothelial function
- Participants will be asked not to change their lifestyle while they are taking part in the study. However, they will be asked not to take any other medications including paracetamol and ibuprofen for the duration of the study.
- Once enrolled to the study subjects will undergo blood pressure, heart rate and EndoPAT tests. Urine and blood will be collected for study analysis.

Eligible participants who have had a COVID-19 vaccination will need to wait at least 4 weeks before entering into any phase of the study.

Participants will be provided with home COVID-19 rapid lateral flow kits. Participants will be asked to perform a test prior to each study visit. Participants with a positive test will be advised to follow government advice, perform PCR test and self-isolate. They will be excluded from the study.

Inclusion/exclusion criteria

Inclusion Criteria	Exclusion Criteria

• Male, 18-40 years old	
• Any history of allergy to NSAIDs or arginine• Significant medical conditions


 • No abnormal findings on medical history, screening, physical examination, haematology, biochemistry, urinalysis and vital signs (sitting blood pressure, resting pulse rate, respiratory rate and body temperature within two weeks of commencement date) • Normal fasting lipid profile (Soverson et al, 1994) • Non-smoking • Clear venous access in upper limbs • BMI 18-30 • No history or signs of drug abuse • No other medication 4 weeks before or during study • Informed written consent 	
 • Pulse rate<50 beats/minute • Sitting systolic blood pressure <80 or >160 mmHg • Sitting diastolic blood pressure <60 or >100 mmHg • Baseline endothelial dysfunction (as defined by EndoPAT; LnRHI<0.51) • Participation in other clinical study 8 weeks before or during study • Donation of blood 8 weeks before or during study • COVID-19 vaccination within 4 weeks • Positive COVID-19 test
---	--

Withdrawal criteria

Participants will be free to withdraw from taking part at any time, and they will be asked to provide a reason for withdrawal which will be recorded but their right to withdraw without providing a reason will be respected. Information collected from participants who have withdrawn may be used, but the investigators will attempt to replace the withdrawn participants with someone who completes the full protocol.

If a subject consents but then fails to fulfil the inclusion/exclusion they will be considered a 'screen failure' and their results will not be used. If screening, or during study visits, results need further follow-up then a medically qualified investigator ([name] or [name]) will contact the general practitioner of the volunteer to request further follow-up.

As the study evaluates, (i) a well-known and relatively safe drug (celecoxib) used in many clinical trial settings, is available on prescription world-wide, and has a similar mechanism of action to ibuprofen and (ii) a drug/supplement (L-arginine) freely available without prescription from high street health food outlets and as a well-tolerated prescription medication for treatment of urea cycle disorders, we do not anticipate that study participants will withdraw due to the study medication.

Re-enrolment

Once participants are enrolled and randomised in the study, the study visits (visits 1 & 2 in phase 1 and visits 3 & 4 in phase 2) need to occur exactly 7 days apart. If participant attends visit 1 but is unable to attend visit 2 for a reason that is unrelated to the study medication e.g. develops an unrelated illness or cannot attend for personal reasons, the participant will have the option to re-enrol as a new participant if there is at least a 4-week washout period if they wish to do so. These participants will need to re-attend screening and re-consent and will be treated as a new participant with a new study number. To avoid double counting, any data obtained from the initial enrolment will not be used and will be superseded by the data generated by re-enrolment.

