8. REGULATORY ISSUES

Ethics Approval

The Study Coordination Centre has obtained approval from the xxx Research Ethics Committee (REC) and Health Research Authority (HRA). The study must also receive confirmation of capacity and capability from each participating NHS Trust before accepting participants into the study or any research activity is carried out. The study will be conducted in accordance with the recommendations for physicians involved in research on human subjects adopted by the 18th World Medical Assembly, Helsinki 1964 and later revisions.

Consent

Consent to enter the study must be sought from each participant only after a full explanation has been given, an information leaflet offered and time allowed for consideration. Signed participant consent should be obtained. The right of the participant to refuse to participate without giving reasons must be respected. After the participant has entered the study the clinician remains free to give alternative treatment to that specified in the protocol at any stage if he/she feels it is in the participant's best interest, but the reasons for doing so should be recorded. In these cases the participants remain within the study for the purposes of follow-up and data

analysis. All participants are free to withdraw at any time from the protocol treatment without giving reasons and without prejudicing further treatment.

Confidentiality

The Chief Investigator will preserve the confidentiality of participants taking part in the study.

All participant information collected during the study will be kept strictly confidential, and any information about participants which leaves the facility will have their name and address removed. Only authorised persons such as researchers, the sponsor and research and development audit will have access to the data.

Study data will be collected using REDCap which is a mature and secure web application for clinical trial data capture. Data is stored on the secure encrypted imperial college server. All data held in REDCap is anonymised. Only members of the research team will have access to data.

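### Do Sections 4 and 8 give opposite rules for the data of a randomised man who takes other medication or meets an exclusion during the study?

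*Combined protocol and SAP*

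**What the plan says.** All references are to the combined protocol and SAP.

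- **Section 4, Withdrawal criteria.** "If a subject consents but then fails to fulfil the inclusion/exclusion they will be considered a" screen failure "and their results will not be used". The sentence gives no time limit. Of men who withdraw, the same part says: "Information collected from participants who have withdrawn may be used". Replacement of withdrawn men will be attempted.
- **Section 4, Inclusion/exclusion criteria.** One inclusion criterion reads "No other medication 4 weeks before or during study". Taking part in another study and donating blood are also barred while the study runs. A positive COVID-19 test is a listed exclusion.
- **Section 4, on COVID-19 testing.** "Participants will be asked to perform a test prior to each study visit". Of men who test positive: "They will be excluded from the study". Nothing is said about data they have already given.
- **Section 8, Consent.** After entry, "the clinician remains free to give alternative treatment to that specified in the protocol at any stage". The consequence for data is: "In these cases the participants remain within the study for the purposes of follow-up and data" analysis.
- **Section 7.** It lists candidate tests and a 5% threshold, and names no intention-to-treat, per-protocol or other set. It gives the effect of celecoxib on endothelial function as the primary endpoint, and places an interim analysis at 20 per group in the washout.

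**The concern.** Taken word for word, the screen-failure sentence has no cut-off at randomisation. Suppose a clinician gives a randomised man a medicine. He has then broken the ban on other medication, so Section 4 would drop his results and Section 8 would keep them. Section 7 does not say which prevails.

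The literal rule would also act backwards. The celecoxib-placebo comparison is complete at Visit 2. If phase 2 goes ahead, a washout of at least 28 days and a further 7 days of treatment follow. A man could have a sound Visit 2 value and lose it for something that happened a month later, possibly after the interim result was known. Two analysts following different sections would then report different primary sets. At stake would be some power, and a conclusion that depends on which section was followed.

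**Working it through.** **1. The texts side by side.** Section 4 sets out the order of events: consent, then a screening assessment that checks the criteria. The screen-failure sentence has the same order (consents, then fails the criteria) and uses the name of that step. Two other rules in Section 4 fit poorly with a wider reading:

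- Recent COVID-19 vaccination is a listed exclusion, yet a vaccinated man only has to wait four weeks before entering any phase. An exclusion that arises mid-study leads to delay, not deletion.
- A positive COVID-19 test has its own consequence, exclusion from the study, with no instruction to discard data. Where the plan means to discard data from an enrolled man, as under Re-enrolment, it says so.

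**2. Width of the overlap.** Section 8 speaks only of treatment given by a clinician. It is silent on self-medication, blood donation, joining another study and COVID-19 tests. The two rules can collide only over a clinician-given medicine after entry.

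**3. The plan's own power.** Inputs from Section 7: effects of 0.80 and 1.06 SD, n = 20 or 40 per group, alpha 0.05 (taken as two-sided). The normal approximation is power = Φ(d√(n/2) − 1.96).

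- n = 20: 71.6% and 91.8% (stated 72-92%).
- n = 40: 94.7% and 99.7% (stated 95-100%).

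The figures reproduce. With the noncentral t distribution, used below, n = 20 gives 69.3% and 90.4%.

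**4. Cost of dropping men.** Noncentral t, df = n1 + n2 − 2, noncentrality d/√(1/n1 + 1/n2):

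| Per arm | Power, 0.80 SD | Power, 1.06 SD |
|---|---|---|
| 20 v 20 | 69.3% | 90.4% |
| 20 v 19 | 68.2% | 89.6% |
| 19 v 19 | 67.0% | 88.9% |
| 18 v 18 | 64.5% | 87.1% |
| 16 v 16 | 59.1% | 82.7% |

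**5. How many men?** The documents give no event rate. Assume that a man has probability p of breaking a criterion, spread evenly over 7 + 28 + 7 = 42 days, with phase 2 going ahead. The share after Visit 2 is 35/42 = 83%.

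| p | Expected loss per arm, 20 × p × 35/42 | Chance of at least one in 40, 1 − (1 − p × 35/42)^40 |
|---|---|---|
| 1% | 0.17 | 28% |
| 2% | 0.33 | 49% |
| 5% | 0.83 | 82% |
| 10% | 1.67 | 97% |

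An expected loss of two per arm needs p = (2/20) × (42/35) = 12%, and four per arm needs 24%. At p = 10%, eight or more losses among 40 men has probability 1.6%. These rates count every kind of breach, so they overstate the Section 4 v Section 8 clash. The even spread is also rough: COVID-19 tests fall before visits, so with equal risk per test two of the three after randomisation (67%) come after Visit 2.

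**6. Error rate and disagreement.** In simulated trials (normal outcome, pooled t-test) each rule used alone has a 5.0% type I error. At 0.80 SD, keeping and dropping disagree on p<0.05 in 4.7% of trials with one man lost and 6.8% with one lost per arm. Always reporting the better of the two would raise the 5.0% to 5.8% and 6.0%.

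**7. Would keeping everyone be better?** Not for other medication before Visit 2. Suppose 1, 2 or 4 of 20 placebo men took an NSAID with a 0.80 SD effect. The expected difference falls to 0.80 × (1 − k/20) = 0.76, 0.72 or 0.64 SD. Simulated power is 64%, 59% or 48% if they are kept, against 68%, 67% or 64% if they are dropped.

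**The case for a change.** The best argument for a change is that the screening-only reading does not close the gap. The during-study parts of three criteria can be broken only after enrolment. A positive COVID-19 test is a listed criterion that Section 4 does apply after randomisation. The screen-failure sentence sits under Withdrawal criteria. If the rule stops at randomisation, the during-study criteria have no stated consequence for data, and withdrawn men's data are covered only by a permissive wording. On either reading Section 7 defines no set, and a decision about a man could be taken after the interim effect is known.

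The textual facts stand: there is no explicit cut-off and no named analysis set. What does not follow is that the plan gives contradictory instructions. Silence about data already recorded is ordinarily resolved by keeping a randomised man's valid Visit 2 value, and Section 8 points that way. The permissive wording on withdrawn men allows that use and does not compete with it. The interim takes the primary comparison during the washout, so phase 2 events cannot affect that look. The concern about choosing a set after seeing results is real in principle, but for one man or one per arm the worst case in step 6 is 5.8% or 6.0%, and it requires always reporting the better result.

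**Conclusion.** The concern does not call for a change. On the natural reading, screen failure means failure at screening, Section 8 governs men treated otherwise after entry, and the trial run as written gives a sound comparison. The missing analysis set is a detail that analysts would fill sensibly.

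On the literal reading the loss is about 1 power point at 0.80 SD for one man and about 2 for one per arm (69.3% to 68.2% and 67.0%), and less at 1.06 SD. Type I error stays at 5% under either rule, provided removal is unrelated to outcome. Losses of 2 to 4 per arm would cost more, but they exceed the 0.17 to 1.67 per arm expected at assumed event rates of 1% to 10%. Those rates, the even spread over time and phase 2 going ahead are assumptions. A rule that keeps every man brings no clear gain in power, since it does worse than dropping when the other medication was taken before Visit 2. A sentence stating that screen failure ends at randomisation would be harmless tidying, but the result does not depend on it.
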